2.2 Hypotheses and/or Estimations

AMG 910 will demonstrate acceptable safety and tolerability in subjects with gastric or GEJ cancer at 1 or more dose levels with at least 1 dose level showing evidence of anti-tumor activity.

3. Study Overview

3.1 Study Design

This is an open-label, ascending, multiple dose, phase 1 study evaluating AMG 910 in subjects with CLDN18.2-positive gastric and GEJ adenocarcinoma. The study will consist of 2 phases:

- Dose-exploration phase
- Dose-expansion phase

3.1.1 Dose Exploration Phase

The dose-exploration phase of the study will estimate the MTD of AMG 910 using a **Bayesian logistic regression model (BLRM)** based on enrollment of 34 gastric cancer subjects. A RP2D may be identified based on emerging safety, efficacy, and pharmacodynamics data prior to reaching an MTD.

AMG 910 will be administered as a short-term IV infusion (approximately 60 minutes) **or as extended IV (eIV) infusion over 96 hours (in cycle 1 week 1) over six 28-day cycles following the doses and dosing schedule outlined in [Table 3-1](#).**

- For cycles 1 and 2, twice a week at days 1 and 3 of each week in a 28-day cycle, **starting with cycle 1 day 8 dose** and

- For cycles 3 to 6, weekly, i.e., days 1, 8, 15, and 22 in a 28-day cycle

Because of the observation of cytokine release syndrome (CRS) events in cohort 1, the dosing of AMG 910 and the dose escalation schedule will be adapted. In cycle 1 week 1, the administration is to start with an approximately 96-hour eIV infusion followed by short-term weekly or twice weekly infusions (approximately 60 minutes) at the planned target doses of AMG 910 of 6.5, 15, 30, 60, 150, 300, 600, 1000, and 2000 µg from cycle 1 week 2 onwards.

For the new dosing schedule with 96-hour eIV infusion of AMG 910, day 1 and day 3 doses of cycle 1 week 1 will be each infused over 48 hours instead of 60 minutes resulting in a total infusion time of 96 hours. It is hypothesized that the eIV infusion approach over a 96-hour period may reduce the intensity and/or frequency of the symptoms associated with CRS associated with the same target dose of AMG 910 when infused twice over a 60-minute duration. The lowest AMG 910 daily dose for eIV administration will be 3.25 µg/day. The calculation of a next higher eIV dose will be based on the following calculation:

Daily eIV dose = total AMG 910 dose, resulting from the twice weekly dosing at the target dose, divided by number of eIV infusion days.

There will be treatment-free intervals of two weeks after cycles 2 and 4. The treatment-free intervals may be extended up to three weeks to allow for recovery in case of adverse events. The treatment-free interval after cycle 4 may also be extended to three weeks for logistical reasons. The maximum treatment duration will be 6 cycles. Subjects who have shown no disease progression and no worsening of performance status at the end of cycle 6 may continue treatment for an additional two cycles if there are no unresolved grade 3 or 4 toxicities and if the investigator and the Amgen Medical Monitor agree that continued treatment may likely provide benefit for the subject.

The DLRT may recommend enrolling more subjects for safety reasons at any point during the study and **the DLRT may explore 2 different AMG 910 dosing schedules in cohorts running in parallel.**

Dose exploration will be conducted in 2 stages: single-subject cohort(s) followed by multiple-subject cohort(s) (3 to 4 subjects per cohort) (Refer: [Table 3-1](#)).

Single subject cohort:

Dose exploration will begin with single-subject cohort(s) and the starting dose is expected to have the first dose C_{max} below MABEL. Serum concentrations to be achieved with first 3 to 4 dose level cohorts are expected to be lower than those at which pharmacodynamic activity translating into treatment-related adverse events or efficacy is predicted to be observed. Therefore, the first two cohorts are pre-planned single subject cohorts. If a subject in the first single-subject cohort does not experience a grade 2 or higher adverse event at least possibly related to AMG 910 or DLT during the initial 28 days of treatment (DLT window for single-subject cohorts), then the next subject may be dosed at the next higher dose level(s) per [Table 3-1](#). Planned doses per cohort level ranging from **2.5** μ g to **2000** μ g. Switching from a single subject cohort to a multiple-subject cohort will occur with cohort 3 or sooner if specific safety criteria are observed as described below during the DLT window:

- DLT or
- Grade ≥ 2 adverse events based on CTCAE version 5.0, at least possibly related to AMG 910, with the exception of lymphopenia or lymphocyte count decreased.

The DLRT will convene to review the safety data and recommend the appropriate dose to be implemented. The recommended dose will not exceed the levels recommended by the BLRM in the dose escalation portion and the next pre-defined dose level. The DLRT may also convene ad hoc meetings any time to review safety data if deemed necessary.

Multiple subject cohort:

Dose escalation in multiple-subject cohorts (3- to 4 subjects per cohort) will begin with single subject cohort and the dose level(s) per [Table 3-1](#). The DLRT will convene to review the safety data and recommend the appropriate dose to be implemented. The recommended dose will not exceed the levels recommended by the BLRM in the dose escalation portion and the next dose level listed in [Table 3-1](#). The DLRT may recommend enrolling more subjects for safety reasons at any point during the study.

For dose escalation with eIV dosing schedule, the DLRT will in addition to the considerations above evaluate the eIV administration and the short-term IV administrations separately for the occurrence of first-dose effects (e.g., CRS and TLS). The DLRT will review the safety data and may recommend to only escalate the dose for either the eIV administration or the short-term infusion administrations for the next cohort. The recommended dose will not exceed the levels recommended by the BLRM in the dose escalation portion and the next dose level

listed in [Table 3-1](#). For subsequent dose escalation decisions, the dose for the elV administration and the short-term IV administrations may be again escalated in parallel while maintaining the relative dose difference or the dose for the not escalated administration may be kept constant.

For multiple-subject cohorts, the DLRT will not recommend dose escalation decisions until each of the following occurs:

- All subjects in the cohort have been followed for safety events for a minimum of 28 days from the first dose of AMG 910 (except if a subject experienced a DLT) or have been followed for a minimum of 72 hours after the 7th dose with treatment interruption not constituting a DLT
- At least 3 of the subjects can be evaluated for DLT assessment

Determination of whether a subject is evaluable for DLT assessment will be made in accordance with the following rules:

- Subjects who receive study treatment (at least 80% of the planned dose for cycle 1) and remain on study through the DLT assessment window will be considered DLT-evaluable.
- Subjects who discontinue from the study prior to completing the DLT assessment window for reasons other than a DLRT will be considered non-evaluable for dose-escalation decisions and MTD determination and may be replaced by an additional subject at that same dose level.

Dose escalation/de-escalation decisions in multiple-subject cohorts will be guided by the BLRM model of dose toxicity. The MTD for BLRM is the dose level predicted to have the highest probability of a DLT rate within the target interval of 20% to 33%, subject to overdose control. To control the risk of overdose, the MTD must have less than a 40% predicted probability of overdosing (DLT rate > 33%). If late onset adverse events (i.e., after the 28-day DLT period) occur or late findings from endoscopic evaluations during a cohort, the DLRT may adaptively re-consider the doses evaluated within a cohort for subsequent dosing and/or possibly trigger a de-escalation or withholding of additional doses in subsequent cohorts. Based on the BLRM model and after reviewing all available safety and tolerability data, the DLRT may recommend dosing at intermediate dose levels between the planned dose levels listed in [Table 3-1](#).

3.1.2 Dose Expansion Phase

Following the dose-exploration phase, a dose-expansion phase will be conducted on 36 additional subjects approximately to confirm safety, PK, and pharmacodynamics at the MTD or RP2D and to obtain further safety and efficacy data and enable correlative biomarker analysis. The dose to be evaluated will be at or below the MTD estimated in the dose exploration cohorts. A final estimate of the MTD and RP2D will be evaluated and confirmed utilizing all DLT-evaluable subjects from the dose exploration and the dose expansion cohorts. This final estimate of the MTD and RP2D will not exceed the MTD identified in the dose escalation portion of the study and will not exceed the MTD identified in the dose escalation portion of the study by the BLRM. Efficacy data will be reviewed in the dose expansion part of the study after the first 15 subjects are enrolled and have had the opportunity to receive at least 8 weeks of treatment and received the first response assessment (with recruitment ongoing).

A final BLRM estimate of the MTD will use all data from dose exploration and dose expansion.

3.1.3 Extension of Treatment Duration

Subjects who have shown no disease progression and no worsening of performance status at the end of cycle 6 may continue treatment for an additional two cycles if there are no unresolved treatment related grade 3 or 4 toxicities and if the investigator and the Amgen Medical Monitor agree that continued treatment may likely provide benefit for the subject. Further extensions of the treatment are to be agreed in the same manner at the end of each second cycle of extended treatment. Treatment schedule and schedule of activities will be conducted as described for cycle 6.

[figure not shown]
Subjects who remain on the treatment for more than 2 years do not need to have additional long-term follow-up. They will complete the study 30 (+3) days following discontinuing treatment.

3.1.4 Re-treatment of Subjects

Subjects who have derived sustained benefit from treatment, meaning at least stable disease and no worsening of performance status, for at least 3 months after the end of treatment but experience relapse or progression thereafter, and have not received any other systemic anti-cancer therapy since their last AMG 910 treatment, may be retreated in a separate retreatment group **for a total of up to 2 rounds of retreatment (up to 6 cycles each)**. Retreatment will be administered at the highest dose level and currently used schedule that has been assessed as safe by the DLRT at the time of retreatment

initiation. Treatment schedule and schedule of activities will be conducted as described for cycles 1 through 6 in the dose exploration and expansion cohorts.

Figure 3-1. Study Schema

LTFU = long-term follow-up; MTD = maximum tolerated dose; RP2D = recommended phase 2 dose

SFU = safety follow-up

^a Multiple-subject cohorts will enroll at a dose level where specific safety and/or efficacy criteria were met in a single-subject cohort or per planned dose level from [Table 3-1](#). For subsequent dose level cohorts, 3-4 total subjects will be enrolled.

^b For cohorts 1b onwards, AMG 910 is administered as extended IV infusion over 96 hours in cycle 1 week 1 and as short-term IV infusions weekly (or twice weekly) starting cycle 1 day 8 onwards in cycle 1 through 6 of 28-day cycles with scheduled 2-week breaks after cycles 2 and 4.

Table 3-1. Planned Doses per Dose Cohort Level

Cohort number	Number of subjects ^a	Dose (µg) Route
(-1)	(3 to 4)	2.5 IV
1	3 to 4	6.5^b IV
1b	3 to 4	6.5^b eIV
2b	3 to 4	15 eIV
3b	3 to 4	30 eIV
4b	3 to 4	60 eIV
5b	3 to 4	150 eIV
6b	3 to 4	300 eIV
7b	3 to 4	600 eIV
8b	3 to 4	1000 eIV
9b	3 to 4	2000 eIV

Routes of administration: eIV = extended intravenous; IV = short-term intravenous.

^a Switching from a single subject cohort to a multiple-subject cohort will occur with cohort 3 or sooner if specific safety criteria are observed as described in Section 6.2.1.1.1 in the protocol.

^b If a dose reduction is needed according to instructions provided in Table 6-3 as in the protocol, treatment will be continued at a dose of 2.5 µg as specified in Section 6.2.2.3.5 as in the protocol.

Note: The “b” cohort numbers are used to differentiate cohorts 1 through 10 denoted in previous versions of the protocol

3.2 Sample Size

It is anticipated that approximately 70 subjects will be enrolled in this study. Up to 34 subjects will be enrolled in the dose-exploration cohorts and up to 36 additional subjects will be enrolled in the dose-expansion cohort.

The sample size in the dose-escalation phase is based on practical consideration and is consistent with conventional oncology studies with the objective to estimate the MTD. With 3 subjects in a cohort, there is a 27% to 70% probability of observing at least 1 DLT if the true DLT rate is 10% to 33% and with 4 subjects in a cohort, there is a 34% to 80% probability.

In the dose-expansion cohort, a subject number of 36 will provide an 84% probability of observing at least 1 adverse event with 5% incidence rate. An exact 95% binomial CI will be provided for overall response rate. With the 36 subjects and 19% overall response rate, the expected 95% CI would be 8% to 36%.

4. Covariates and Subgroups

4.1 Planned Covariates

Not applicable.

4.2 Subgroups

Not applicable.

5. Definitions

Adverse events

An adverse event (**AE**) is any untoward medical occurrence in a clinical study subject irrespective of a causal relationship with the study treatment.

Age at enrollment

Subject age at enrollment will be determined using the age in years reported in the clinical database.

Area under the Curve (AUC)

The area under the **serum** drug concentration-time curve (AUC) reflects the actual body exposure to drug after administration of a dose of the drug.

Baseline

For any variable, unless otherwise specified, the baseline is the last non-missing assessment taken prior to the first administration of AMG 910.

For parameters/assessments not scheduled to be performed (or scheduled but not performed) on the same day as the first administration of AMG 910, the baseline value is the value from the screening period measured closest to the day of first administration of AMG 910.

Baseline ECG values in triplicate

The mean of values in a triplicate should be calculated for Baseline. Baseline triplicate value is the mean of all pre-dose assessments. For all post- baseline ECG, the mean value for measurements taken at the same assessment will be calculated and used in the analysis.

When an ECG is missing within a triplicate, all available data will be averaged for that time point.

Best Overall Response (BOR) - using RECIST v1.1 criteria

BOR is defined as the best response in the following order: CR, PR, SD, PD, or NE, where CR and PR require confirmation by a repeat consecutive assessment at least 4 weeks after the first detection of radiographical response or progressive disease. Confirmation of SD, minimum 6 weeks duration from the baseline scan is required. The details of derivation of BOR is described in [Appendix B](#).

Complete response (CR) per RECIST v1.1 criteria

Disappearance of all target lesions, non-target lesions and normalization of tumor markers. Any pathological lymph nodes (whether target or non-target) must have reduction in short axis to <10 mm.

Objective Response Rate (ORR) per RECIST v1.1 criteria

Objective response rate is defined as the proportion of patients with a BOR of CR or PR.

Partial Response (PR) per RECIST v1.1 criteria

Partial Response (PR) is defined as at least a 30% decrease in the sum of diameters of target lesions, taking as reference the baseline sum diameters. Non target lesions must be non-Progressive Disease (non-PD).

BMI

Body Mass Index should be calculated using the following formula:

$$\text{BMI (kg/m}^2\text{)} = \text{weight (kg)} / [\text{height (cm)} / 100]^2$$

Change from Baseline

Change from Baseline is the arithmetic difference between post-dose assessments and Baseline value.

$$\text{Change (absolute) from Baseline} = (\text{Post-baseline Value} - \text{Baseline Value})$$

$$\text{Change (percent) from Baseline} = [(\text{Post-baseline Value} - \text{Baseline Value}) / \text{Baseline Value}] \times 100$$

C}_{\text{max}}

Maximum observed drug concentration.

C}_{\text{min}}

Minimum observed drug concentration.

Dose Limiting Toxicity

Dose limiting toxicities are defined as any adverse events at least possibly related to AMG 910 with an onset within the first 28 days following first dose for single-subject cohorts and within the safety observation period for multiple-subject cohorts as defined in section 6.2.1.1.3 of the protocol.

Additional information on DLTs are given in the section 6.2.1.1.2 of the protocol.

End of study (End of trial)

It is defined as the date when the last subject across all sites is assessed or receives an intervention for evaluation in the study (i.e., last subject last visit), following any additional parts in the study (e.g., long-term follow-up), as applicable.

Fridericia-corrected QT intervals (QTcF)

The Fridericia correction will be calculated from the investigator reported QT (msec) and RR interval (msec), as follows:

$$\text{QTcF} = \text{QT}/(\text{RR}/1000)^{1/3}$$

Investigational product (IP)

The term 'investigational product' is used in reference to AMG 910.

Last investigational product dose date

The last IP date for each subject is defined as the latest date IP administered.

Long term follow-up (LTFU)

Subjects will be followed for every 6 months up to 2 years from the first dose of AMG 910 for all subjects who have not withdrawn consent by clinic visit, telephone or chart review to assess for survival and/or the commencement of subsequent cancer therapy. **Subjects who remain on the treatment for more than 2 years do not need to have additional long-term follow-up (LTFU). They will complete the study 30 (+3) days following discontinuing treatment.**

Maximum Tolerated Dose (MTD)

A final estimate of the MTD will be made based on a Bayesian Logistic Regression Model (BLRM) utilizing all DLT-evaluable subjects from the dose exploration and dose expansion cohorts. The MTD for BLM is the dose level predicted to have the highest probability of a DLT rate within the target interval of 20% to 33%, subject to overdose control. To control the risk of overdose, the MTD must have less than a 40% predicted probability of overdosing (DLT rate >33%).

Primary completion

The primary completion date is the date when data for the primary endpoint are last collected for the purposes of conducting the primary analysis. It is the date when the last subject is assessed or receives AMG 910 for the final collection of data for the primary endpoint(s), for the purposes of conducting the primary analysis, whether the study concluded as planned or was terminated early.

Safety follow-up

It is defined as the subject visit at least 30 (+3) days after last dose of AMG 910 is received to assess the risk of delayed adverse events.

Serious adverse event

A Serious Adverse Event is defined as any untoward medical occurrence that, meets at least 1 of the following serious criteria:

- Results in death (fatal).
- Immediately life-threatening.
- Requires in-patient hospitalization or prolongation of existing hospitalization.
- Results in persistent or significant disability/incapacity.
- Other medically important serious event.
- Is a congenital anomaly/birth defect.

Study day

Post-study day: study day= (date – date of Study Day 1) + 1.

Pre-study day: study day= (date – date of Study Day 1).

Study day 1

It is defined as the first day that AMG 910 is administered to the subject.

Treatment emergent adverse event

A treatment - emergent adverse event (**TEAE**) is any adverse event starting on or after the first administration of investigational product, as determined by the flag indicating if the adverse event started prior to the first dose on the Events CRF, and up to and including 30 days after the last IP dose date. The severity of each adverse event will be graded using the CTCAE version 5.0. Adverse events will be coded using MedDRA.

Treatment related adverse event

A treatment-related AE is any treatment-emergent AE that per investigator review has a reasonable possibility of being caused by AMG 910.

6. Analysis Sets

The following sub-sections describe the analysis sets to be used.

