4.1 Overall Design

This is an open-label, ascending, multiple dose, phase 1 study evaluating AMG 910 in subjects with CLDN18.2-positive gastric adenocarcinoma. The study will consist of:

- Dose-exploration phase
- Dose-expansion phase

The dose-exploration phase of the study will estimate the MTD of AMG 910 using a **Bayesian logistic regression model** (BLRM). A RP2D may be identified based on emerging safety, efficacy, and pharmacodynamic data prior to reaching an MTD.

Following the dose-exploration phase, a dose-expansion phase will be conducted to confirm safety, PK, and pharmacodynamics at the MTD or RP2D and to obtain further safety and efficacy data and enable correlative biomarker analysis.

Because of the observation of cytokine release syndrome (CRS) events in cohort 1, the dosing of AMG 910 and the dose escalation schedule will be adapted and AMG 910 will be administered in cycle 1 week 1 as an extended intravenous (IV) infusion (eIV) for 96 hours starting on day 1 followed by weekly short-term IV infusions (approximately 60 minutes) for all cycles of subjects enrolled in next cohorts (cohorts 1b and beyond).

Furthermore, the following modifications may be recommended by the Dose Level Review Team (DLRT) depending on the observed safety and efficacy observed in all prior cohorts:

- **To adapt duration of eIV administration during cycle 1 week 1 within a range of 3 to 7 days**
- **To switch to the twice weekly dosing schedule after cycle 1 week 1 and administer AMG 910 as follows:**
 - For cycles 1 and 2, twice a week at days 1 and 3 of each week in a 28-day cycle, **starting with cycle 1 day 8 dose** and
 - For cycles 3 to 6, weekly, ie, days 1, 8, 15, and 22 in a 28-day cycle

There will be treatment-free intervals of 2 weeks after cycles 2 and 4.

The treatment-free intervals may be extended up to 3 weeks to allow for recovery in case of adverse events. The treatment-free interval after cycle 4 may also be extended to 3 weeks for logistical reasons.

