- The MTD is identified. A dose level is considered the MTD when the BLRM recommends treatment at this dose level and 6 or more evaluable subjects have already been treated at this dose level.

- On the basis of a review of real-time safety data and available preliminary PK data, dose escalation may be halted or modified by the Sponsor as deemed appropriate. A re-evaluation of the risk/benefit for the study will be necessary after the following observations:
 - Gastrointestinal events of CTCAE grade 3 in 2 subjects, with the exemption of nausea, vomiting, and abdominal pain, and gastrointestinal events of CTCAE grade 4 in 2 subjects if events are at least possibly related to AMG 910
 - Gastrointestinal event of CTCAE grade 5 in 1 subject, at least possibly related to AMG 910

To acquire additional safety and pharmacodynamic data to better inform the RP2D, additional subjects may be enrolled at a dose level that has been shown to not exceed the MTD based on the dose-escalation criteria described above, and at which there is evidence of anti-tumor activity and/or pharmacodynamic biomarker modulation. Up to approximately 3 additional subjects per dose level may be enrolled.

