6.2.1.2 Dose-expansion Phase

Upon completion of the dose exploration part of the study, up to approximately 36 additional subjects will be enrolled in the dose expansion part to gain further clinical experience, safety and efficacy data for AMG 910 in subjects with gastric adenocarcinomas. The dose to be evaluated will be at or below the MTD estimated in the dose exploration cohorts. A final estimate of the MTD and RP2D will be evaluated and confirmed utilizing all DLT-evaluable subjects from the dose exploration and the dose expansion cohorts. This final estimate of the MTD and RP2D will not exceed the MTD identified in the dose escalation portion of the study and will not exceed the MTD identified in the dose escalation portion of the study by the BLRM. Efficacy data will be reviewed in the dose expansion part of the study after the first 15 subjects are enrolled and have had the opportunity to receive at least 8 weeks of treatment and received the first response assessment (with recruitment ongoing). Dose expansion may be discontinued early; the guidelines for early stopping due to insufficient efficacy and the guidelines for early stopping due to excessive toxicity are detailed in Section 9.4.1.1. The DLRT may also convene ad hoc meetings any time to review safety data if deemed necessary. A final BLRM estimate of the MTD will use all data from dose exploration and dose expansion.

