^b If no institutional ULN is specified, age/sex ULN creatinine may be defined as follows: > 1 to < 12 years of age, both male and female, 61.6 $\mu\text{mol/L}$; ≥ 12 to < 16 years, both male and female, 88 $\mu\text{mol/L}$; ≥ 16 years, female 105.6 $\mu\text{mol/L}$, male 114.4 $\mu\text{mol/L}$

**11.15 Appendix 15. Protocol Amendment 2 Schedule of Activities (SoA)
for Cohort 1**

Table 1-1. Schedule of Activities

Week	SCR ^a	Treatment Cycle 1																						
		1					2					3					4							
Cycle Day		1	2	3	4	5	8	9	10	11	15	16	17	18	22	23	24	25						
Hour (relative to EOI ^b)		PRE 0	EOI 4	24	PRE 0	EOI 4	24	48	PRE 0	EOI 4	24	PRE 0	EOI 4	24	PRE 0	EOI 4	24	PRE 0	EOI 4	24	PRE 0	EOI 4		
GENERAL AND SAFETY ASSESSMENTS																								
Informed consent	X																							
Clinical evaluation ^c	X	X		X	X		X	X	X		X	X		X	X		X	X		X	X	X		
Vital signs, pulse oximetry	X	X	X ^d	X	X ^d	X	X	X ^d	X	X ^d	X	X ^d	X	X ^d	X	X ^d	X	X ^d	X	X ^d	X	X ^d		
12-lead ECG ^c triplicate	X	X	X	X	X		X	X	X	X	X	X	X	X					X		X			
Adverse events review																								
Serious adverse events review																								
Prior/concomitant medication																								
LOCAL LABORATORY ASSESSMENTS																								
Pregnancy test ^c	X	X																						
HIV, Hepatitis B and C screening	X																							
CBC with differential	X	X		X	X	X		X	X	X		X	X	X		X	X		X	X	X	X		
Coagulation	X	X		X	X	X		X	X	X		X	X	X		X	X		X	X	X	X		
Chemistry panel	X	X		X	X	X		X	X	X		X	X	X		X	X		X	X	X	X		
Urinalysis	X			X										X										
Gastroscopy ^c	X ^d												X ^d											
CENTRAL LABORATORY ASSESSMENTS																								
STUDY TREATMENT AND OTHER ASSESSMENTS / PROCEDURES																								
Imaging																								
AMG 910 short term IV infusion		X			X			X		X		X		X		X		X		X		X		
Hospital stay			From Day 1 until 48 hours after EOI on Day 3					Until 48 hours after EOI on Day 8 and Until 24 hours after EOI on Day 10					Until 24 hours after EOI on Day 15			Until 24 hours after EOI on Day 17			Until 24 hours after EOI on Day 22			Until 24 hours after EOI on Day 24		

Page 1 of 5

Abbreviations and footnotes defined on last page of table

Table 1-1. Schedule of Activities

Week	Treatment Cycle 2 ^l																							
	1				2				3				4											
Cycle Day	1	3	8	10	15	17	22	24	PRE	0	EOI	4	PRE	0	EOI	4	PRE	0	EOI	4	PRE	0	EOI	4
GENERAL AND SAFETY ASSESSMENTS																								
Clinical evaluation ^c	X		X	X	X	X	X	X	X	X	X	X	X	X	X	X	X	X	X	X	X			

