6.3 Study Specific Analyses Set(s)

6.3.1 DLT Analyses Set(s)

Dose limiting toxicity will be performed on the DLT Analysis set. DLT Analysis **set** is defined as all subjects that are enrolled and receive at least 1 dose of AMG 910 with an evaluable DLT endpoint.

The DLT endpoint is evaluable if either: 1) the subject experiences a DLT, or 2) the subject does not experience a DLT within the DLT window in effect for the dose level cohort of the subject.

A non-evaluable subject may be replaced by an additional subject at the same dose level for dose-escalation and MTD determination.

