9.6 Safety Analyses

9.6.1 Analyses of Primary Safety Endpoints

Unless otherwise specified, statistical analyses on safety endpoints will be done using subjects from the Safety Analysis Set, which includes subjects that are enrolled and received at least 1 dose of AMG 910.

The analysis of DLTs will be conducted on the DLT Analysis Set. The probability of a subject having a DLT by planned dose level will be estimated using a two-parameter BLRM model.

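### The final BLRM pools cohort 1 (short-term IV start) with the eIV cohorts under dose alone, so the DLT probabilities and MTD it reports do not belong to the eIV regimen

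*SAP*

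**What the plan says.** - **Data in the model.** The MTD definition in SAP Section 5 reads "A final estimate of the MTD will be made based on a Bayesian Logistic Regression Model (BLRM) utilizing all DLT-evaluable subjects" and covers both phases. Protocol 6.2.1.2 agrees: "A final BLRM estimate of the MTD will use all data from dose exploration and dose expansion". The DLT Analysis Set (SAP 6.3.1) is "all subjects that are enrolled and receive at least 1 dose of AMG 910 with an evaluable DLT endpoint"; nothing in it refers to route or schedule.
- **Model.** SAP 9.6.1: "The probability of a subject having a DLT by planned dose level will be estimated using a two-parameter BLRM model". SAP 4.1 plans no covariates, so there is no regimen term.
- **Regimens.** SAP Table 3-1 gives cohort 1 as 6.5 µg IV and cohort 1b as 6.5 µg eIV. The cohort 1 schedule in protocol Appendix 15 lists "AMG 910 short term IV infusion", twice weekly in cycle 1. (Protocol Table 6-2 prints eIV against cohort 1. Appendix 15 and the SAP table show otherwise.)
- **Reason for the change.** Protocol 4.1 begins its explanation with "Because of the observation of cytokine release syndrome (CRS) events in cohort 1". SAP 3.1.1 hypothesizes that the eIV start "may reduce the intensity and/or frequency of the symptoms associated with CRS associated with the same target dose of AMG 910 when infused twice" over 60 minutes.
- **MTD rule.** The MTD is the level most likely to have a DLT rate of 20% to 33%, with less than a 40% chance that the rate exceeds 33%. Protocol 6.2.1.1.2 also requires that "6 or more evaluable subjects have already been treated at this dose level".

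**The concern.** Severe CRS counts towards the DLT endpoint: protocol 6.2.1.3 includes non-hematologic events of grade 3 or higher, and Appendix 13 refers grade 3 and 4 CRS to that section. A start that changes CRS can therefore change the DLT risk at the same nominal dose. A model with dose as its only variable cannot show this.

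Determining the MTD and/or RP2D is a primary objective. SAP 7.1 says that the study was terminated early and that one combined final analysis remains; SAP 9.6.1 still plans the BLRM in it. Any DLT from the abandoned start would enter the fitted probability at every dose level, including levels given only with the eIV start. The table from that fit would carry no sign that two regimens lie behind it.

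**Working it through.** **Inputs.** Protocol Appendix 9 gives ln(a) ~ N(−0.847, SD 1.275), ln(b) ~ N(−1.098, SD 1.981), correlation 0, and reference dose 3500 µg. The model is logit p(d) = ln(a) + b·ln(d/3500). Dose levels are those of SAP Table 3-1. The cohort 1 DLT count is **not given**, so 0 to 3 of 3 is assumed. The eIV results below are illustrative.

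**Reproducing the plan's figures.**
- At the prior means, b = exp(−1.098) = 0.3335 and ln(6.5/3500) = −6.289. The logit at 6.5 µg is −0.847 − 0.3335 × 6.289 = −2.944, so p = 0.050. At 3500 µg the logit is −0.847, so p = 0.300. Both agree with Appendix 9.
- Integrating over the prior gives P(p ≤ 0.40 at 6.5 µg) = 0.896 (stated 0.90) and P(p ≤ 0.05 at 3500 µg) = 0.05 (stated 0.05).

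**How far one label stretches.**
- First-dose input rate: 6.5 µg over about 1 hour against 3.25 µg/day, or 6.5/(3.25/24) = 48-fold.
- Week 1 total: 2 × 6.5 = 4 × 3.25 = 13 µg in both cohorts.
- Cycle 1 total: cohort 1, 8 × 6.5 = 52 µg. Cohort 1b weekly, 13 + 3 × 6.5 = 32.5 µg. Cohort 1b twice weekly, 13 + 6 × 6.5 = 52 µg. The totals differ only under weekly dosing.

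**Refitting with and without cohort 1.** The BLRM level is the dose with the highest P(0.20 < p ≤ 0.33) among doses with P(p > 0.33) < 0.40. The capped next dose also applies the limit of one planned level above the current one (protocol 6.2.1.1.2). The eIV data are:
- Example 1: 0/3 at 6.5, 15 and 30 µg.
- Example 2: 0/3 at 6.5 µg.
- Example 3: 0/3 at each level from 6.5 to 150 µg, 2/6 at 300 µg.
- Example 4: 0/3 at each level from 6.5 to 300 µg, 2/6 at 600 µg.

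| Example and quantity | eIV alone | + 0/3 | + 1/3 | + 2/3 | + 3/3 |
|---|---|---|---|---|---|
| 1: mean p at 30 µg | 2.8% | 2.2% | 11.8% | 18.8% | 25.6% |
| 1: BLRM level (µg) | 2000 | 2000 | 2000 | 300 | 60 |
| 1: capped next dose (µg) | 60 | 60 | 60 | 60 | 60 |
| 2: P(p > 0.33) at 6.5 µg | 2.5% | 0.6% | 10.4% | 34.1% | 64.3% |
| 2: BLRM level (µg) | 2000 | 2000 | 300 | 15 | none |
| 2: capped next dose (µg) | 15 | 15 | 15 | 15 | none |
| 3: BLRM level (µg) | 1000 | 1000 | 1000 | 600 | 300 |
| 3: capped next dose (µg) | 600 | 600 | 600 | 600 | 300 |
| 4: P(p > 0.33) at 2000 µg | 35.3% | 36.7% | 18.1% | 15.4% | 18.1% |
| 4: BLRM level (µg) | 1000 | 1000 | 2000 | 2000 | 1000 |
| 4: capped next dose (µg) | 1000 | 1000 | 1000 | 1000 | 1000 |

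**Reading the table.**
- One cohort 1 DLT raises the mean probability at 30 µg from 2.8% to 11.8%, about fourfold, with the same eIV data.
- With no cohort 1 DLT, the BLRM level is the same as for eIV alone in all four examples.
- Under the cap, the next dose moves only at 3/3, in examples 2 and 3. In example 3 the MTD rule is then met at 300 µg.
- Pooling is not always cautious. In example 4, DLTs at the lowest dose flatten the fitted slope and lower the overdose probability at 2000 µg.

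**6-subject count.** Only 6.5 µg is shared. Cohorts 1 and 1b have 3 to 4 subjects each, so a count by dose level could reach 6 to 8 with only 3 to 4 on the eIV start.

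**The case against.** The case for leaving the plan alone has several sound parts.

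- **Escalation was protected.** A reader might infer from the uncapped levels that pooling would send the trial to a wrong dose. The documents do not support that. The next-level cap removes almost all of the shift, and protocol 6.2.1.1.2 has the DLRT review first-dose effects of the eIV and short-term parts separately. Protocol 6.2.1.2 and SAP 3.1.2 also hold the final MTD at or below the escalation MTD, which limits the rise in example 4. This stands.
- **High cohort 1 counts may be implausible.** The documents report CRS events but neither grades nor DLTs, so a reader cannot infer that cohort 1 had DLTs. With this prior, cohort 1 alone at 2/3 or 3/3 gives P(p > 0.33) of 0.68 or 0.92 at 6.5 µg, and no level is admissible. Yet cohort 1b re-entered at 6.5 µg. Either the count was at most about 1, or the amendment set the model aside. This is only inference, but it favours the left side of the table.
- **Cohort 1 remains informative.** Week 1 totals match, and from day 8 the eIV cohorts also receive 60-minute infusions. No document claims that gastric toxicity depends on infusion rate. This argues for keeping the pooled fit in view, not for making it the only fit.
- **Results are shown by schedule elsewhere.** SAP 9.1 plans descriptive statistics by dose and schedule, and SAP 9.6.2 plans adverse event tables by cohort and dose. Neither changes what enters the BLRM.
- **Pooling is the protocol's own analysis.** So SAP Section 10 is not wrong in reporting no change.

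**Conclusion.** The concern holds for the final model estimate. The plan fits all DLT-evaluable subjects on dose alone, while the SAP itself gives a reason why the risk at 6.5 µg may differ between the two starts. The reported DLT probabilities, a primary-endpoint result, would then describe a mixture of regimens.

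The size depends on the cohort 1 count. At 30 µg in example 1, pooling moves the mean from 2.8% to 2.2% with no cohort 1 DLT, to 11.8% with one, and to 25.6% with three. These figures rest on the Appendix 9 prior, 3 subjects in cohort 1 and illustrative eIV results.

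Two further readings go too far. A reader might take the 6-subject count to pool both starts by rule; the text only says dose level and does not mention regimen, the planned-dose tables list the cohorts as separate rows, and only 6.5 µg is affected. A reader might also say that the SAP expects less toxicity with eIV; it hypothesizes a possible reduction, and only in CRS symptoms.

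This should be fixed before the combined final analysis.

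**What to change.** 1. In SAP Section 5 (MTD) and 9.6.1, fit the existing BLRM to eIV-start subjects (cohorts 1b onward, plus any expansion) for the eIV regimen's DLT probabilities and MTD.
2. Report cohort 1 DLTs as a separate row with the exact 95% CI. The interval will be wide: for 0/3 its upper limit is 1 − 0.025^(1/3) = 70.8%.
3. Present the protocol's all-data fit beside it as a sensitivity analysis.
4. List the change in SAP Section 10.
5. State that the 6-subject count at 6.5 µg means eIV-start subjects.
6. As a clarification only: protocol 6.2.1.1.2 lets the DLRT escalate the eIV or the short-term dose alone. If such a cohort was enrolled, state which dose labels it in the model and report the MTD as a pair of doses; if none was, say so.

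**Cost.** Two sentences, one line in SAP Section 10 and one extra run; the prior and decision rule stay as they are, and no new data are needed. The eIV fit loses the 3 to 4 cohort 1 subjects. It also still pools weekly with twice-weekly dosing, and eIV durations of 3 to 7 days, wherever those options were used. The SAP should state that limit.
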